5.17.2. Changes to the Analysis Plan

This analysis plan is an update to version 3.0 (09 August 2019). The main changes to version 3.0 of the Statistical Analysis Plan are:

- 1) Remove stratification of Generation 1 and 2 from all analyses
- Include an extra definition and summary of Thrombotic Events using a broader list of preferred terms, per FDA request
- 3) Reclassify Urinary Bleeds from the "GI" category to the "Other" category
- 4) Pre-specify an analysis of the
 - a. correlation between reversal of anti-fXa activity with effective hemostasis, and
 - b. correlation between reversal of anti-fXa activity with mortality

Previous Changes to SAP

The previous analysis plan was an update to versions 1.0 (30 October 2018) and 2.0 (21 November 2018). The main purpose of changes to the versions 1.0 and 2.0 of the Statistical Analysis Plan was to accommodate additional patients treated with edoxaban and patients in Japan, and to align the SAP with the last version of the protocol (i.e., amendment 5 and 6).

The main change to the SAP (as in the protocol) regards the definition of efficacy evaluable patient population to include requirement of a minimum anti-fXa activity level for edoxaban as follows:

The Efficacy Population will include all patients in the Safety Population who meet all of the following criteria:

- · Are determined by the EAC to meet the clinical bleeding inclusion criteria.
- Have a baseline anti-fXa level
- Baseline anti-fXa level of at least 75 ng/mL for apixaban and rivaroxaban, 40 ng/mL for edoxaban, or 0.25 IU/mL for patients receiving enoxaparin.

7.0 LIST OF TABLES

Sample tables listed below. These will not be updated with changes.

Table Number	Table Title
Table 14.1.1.1	Table 14.1.1.1 Patient Enrollment by Protocol Version (Safety Population)
Table 14.1.1.2	Table 14.1.1.2. Baseline Characteristics (Safety and Efficacy Population)
Table 14.1.1.3a	Table 14.1.1.3a. Baseline Characteristics by Generation (Safety Population)
Table 14.1.1.3b	Table 14.1.1.3b. Baseline Characteristics by Generation (Efficacy Population)
Table 14.1.1.3c	Table 14.1.1.3c. Baseline Characteristics by Region (Safety Population)
Table 14.1.1.3d	Table 14.1.1.3d. Baseline Characteristics by Region (Efficacy Population
Table 14.1.1.4	Table 14.1.1.4. Medical History by Andexanet Generation (Safety Population)
Table 14.1.1.5	Table 14.1.1.5. Medical History by Region (Safety Population)
Table 14.1.1.6	Table 14.1.1.6. Details of Hospitalization (Safety and Efficacy Populations)
Table 14.1.1.7	Table 14.1.1.7. Anti-platelet & NSAID Agents Administered Prior to Andexanet Treatment
Table 14.1.1.8	Table 14.1.1.8. Hemoglobin Over Time (Safety Population)
Table 14.1.1.9	Table 14.1.1.9 Baseline Cockcroft-Gault Creatinine Clearance (Safety and Efficacy Populations)
Table 14.1.1.10	Table 14.1.1.10. Baseline Characteristics of Systolic Blood Pressure, Diastolic Blood Pressure, and Heart Rate Over Time by Bleed Type (Safety Population)
Table 14.1.1.11	Table 14.1.1.11. Hemodynamic Compromise Signs at 3 Hours Before Bolus & 15 Minutes Before Bolus (Safety Population)
Table 14.1.1.12a	Table 14.1.1.12a. Baseline Prognostic Clinical Indicators in Patients with ICH by Region (Safety Population)
Table 14.1.1.12b	Table 14.1.1.12b. Baseline Prognostic Clinical Indicators in Patients with ICH by Region (Efficacy Population)
Table 14.1.1.12c	Table 14.1.1.12c. Baseline Prognostic Clinical Indicators in Patients with ICH by Generation (Safety Population)
Table 14.1.1.12d	Table 14.1.1.12d. Baseline Prognostic Clinical Indicators in Patients with ICH by Generation (Efficacy Population)
Table 14.1.1.12e	Table 14.1.1.12e. Baseline Prognostic Clinical Indicators in Patients with ICH (Safety & Efficacy Population)
Table 14.1.1.13a	Table 14.1.1.13a. Summary of Patients Enrolled by FXa Inhibitor and Primary Bleed Type (Safety Population)
Table 14.1.1.13b	Table 14.1.1.13b. Summary of Patients Enrolled by Age Group and Primary Bleed Type (Safety Population)
Table 14.1.1.14	Table 14.1.1.14. Time (Hours) from the last dose of FXa Inhibitor to Start of Andexanet Treatment (Safety Population)
Table 14.1.1.15	Table 14.1.1.15. Pre-dose Treatment of Bleeding Episode by Region (Safety Population)
Table 14.1.1.16	Table 14.1.1.16. Coagulation and Biochemistry at 3 Hours Before Bolus (Safety Population)
Table 14.1.1.17	Table 14.1.1.17. Baseline Anatomic Characteristics of Intracranial Hemorrhage by Bleeding Compartment (Safety and Efficacy Population)

Table Number	Table Title
Table 14.2.1.1a	Table 14.2.1.1a. Summary for Anti-fXa Activity by FXa Inhibitor (Efficacy Population)
Table 14.2.1.1b	Table 14.2.1.1b. Summary for Anti-fXa Activity by FXa Inhibitor (Safety Population)
Table 14.2.1.2a	Table 14.2.1.2a. Summary for Anti-fXa Activity (ng/mL) for Patients who Received Apixaban (Efficacy Population)
Table 14.2.1.2b	Table 14.2.1.2b. Summary for Anti-fXa Activity (ng/mL) for Patients who Received Rivaroxaban (Efficacy Population)
Table 14.2.1.2c	Table 14.2.1.2c. Summary for Anti-fXa Activity (ng/mL) for Patients who Received Enoxaparin (Efficacy Population)
Table 14.2.1.2d	Table 14.2.1.2d. Summary for Anti-fXa Activity (ng/mL) for Patients who Received Edoxaban (Efficacy Population)
Table 14.2.1.3	Table 14.2.1.3. Summary for Anti-fXa Activity for patients with Supratherapeutic Values by FXa Inhibitor (Efficacy Population)
Table 14.2.1.4	Table 14.2.1.4. Patients with Baseline Anti-fXa Activity of Apixaban >300 ng/mL and of Rivaroxaban >210 or >400 ng/mL (Low and High Andexanet Doses) (Efficacy Population)
Table 14.2.1.5	Table 14.2.1.5. Summary of Baseline Anti-fXa Activity of Apixaban >300 ng/mL and of Rivaroxaban >210 or >400 ng/mL (Low and High Andexanet Doses) (Efficacy Population)
Table 14.2.1.6a	Table 14.2.1.6a. Summary for Anti-fXa Activity (ng/mL) for Patients who Received Apixaban by Generation (Efficacy Population)
Table 14.2.1.6b	Table 14.2.1.6b. Summary for Anti-fXa Activity (ng/mL) for Patients who received Rivaroxaban by Generation (Efficacy Population)
Table 14.2.1.6c	Table 14.2.1.6c. Summary for Anti-fXa Activity (ng/mL) for Patients who received Edoxaban by Generation (Efficacy Population)
Table 14.2.1.6d	Table 14.2.1.6d. Summary for Anti-fXa Activity (IU/mL) for Patients who received Enoxaparin by Generation (Efficacy Population)
Table 14.2.2.1a	Table 14.2.2.1a. Hemostatic Efficacy at 12 Hours Post Andexanet (Efficacy Population)
Table 14.2.2.1b	Table 14.2.2.1b. Hemostatic Efficacy at 12 Hours Post Andexanet (Safety Population)
Table 14.2.2.1c	Table 14.2.2.1c. Analyses of Hemostatic Efficacy at 12 Hours Post Andexanet (Efficacy Population)
Table 14.2.2.2	Table 14.2.2.2. Hemostatic Efficacy at 12 Hours Post Andexanet by Subgroup (Efficacy Population)
Table 14.2.2.3	Table 14.2.2.3. Hemostatic Efficacy by Andexanet Generation
Table 14.2.2.4	Table 14.2.2.4. Anti-fXa Activity by Hemostatic Efficacy (Efficacy Population)
Table 14.2.2.5a	Table 14.2.2.5a. Hemostatic Efficacy at 12 Hours Post Andexanet by Baseline Anti- fXa Activity of Apixaban and Rivaroxaban (Safety Population)
Table 14.2.2.5b	Table 14.2.2.5b. Hemostatic Efficacy at 12 Hours Post Andexanet by Baseline Anti-fXa Activity of Enoxaparin (Safety Population)

Table Number	Table Title
Table 14.2.2.5c	Table 14.2.2.5c. Hemostatic Efficacy at 12 Hours Post Andexanet by Baseline Anti- fXa Activity of Edoxaban (Safety Population)
Table 14.2.2.6	Table 14.2.2.6. Distribution of Excellent, Good, and Poor/None Hemostatic Efficacy by FXa Inhibitor and Percentage Reduction in Anti-fXa Activity (Efficacy Population)
Table 14.2.2.7	Table 14.2.2.7. Summary of Possible Confounders Between Anti-fXa Activity and Hemostatic Efficacy (Efficacy Population)
Table 14.2.2.8	Table 14.2.2.8. Distribution of Excellent, Good, and Poor/None Hemostatic Efficacy at 12 Hours Post Andexanet by Subgroup (Efficacy Population)
Table 14.2.2.9	Table 14.2.2.9. Hemostatic Efficacy of Evaluable or non-Evaluable Patients at 12 Hours Post Andexanet (Efficacy Population)
Table 14.2.3.1a	Table 14.2.3.1a. Relationship between Anti-fXa Activity and Hemostatic Efficacy for Patients who Received Apixaban or Rivaroxaban
Table 14.2.3.1b	Table 14.2.3.1b. Odds Ratio for Anti-fXa Activity and Hemostatic Efficacy for Patients who Received Apixaban or Rivaroxaban
Table 14.2.3.2a	Table 14.2.3.2a. Relationship between Anti-fXa Activity and Hemostatic Efficacy for Patients with ICH who Received Apixaban or Rivaroxaban
Table 14.2.3.2b	Table 14.2.3.2b. Odds Ratio for Anti-fXa Activity and Hemostatic Efficacy for Patients with ICH who Received Apixaban or Rivaroxaban
Table 14.2.3.5	Table 14.2.3.5. Effect of Baseline Characteristics on the Relationship between Anti- fXa Activity and Hemostatic Efficacy in Patients with ICH (Apixaban and Rivaroxaban)
Table 14.2.4.1a	Table 14.2.4.1a. Free (Unbound) Plasma Concentration (ng/mL) Over Time of Apixaban (Efficacy Population)
Table 14.2.4.1b	Table 14.2.4.1b. Free (Unbound) Plasma Concentration (ng/mL) Over Time of Rivaroxaban (Efficacy Population)
Table 14.2.4.1c	Table 14.2.4.1c. Free (Unbound) Plasma Concentration (ng/mL) Over Time of Edoxaban (Efficacy Population)
Table 14.2.4.2a	Table 14.2.4.2a. Endogenous Thrombin Potential & Non TF Endogenous Thrombin Potential (Efficacy Population)
Table 14.2.4.2b	Table 14.2.4.2b. Endogenous Thrombin Potential & Non TF Endogenous Thrombin Potential Over Time (Efficacy Population)
Table 14.2.4.2c	Table 14.2.4.2c. Endogenous Thrombin Potential Parameters (Efficacy Population)
Table 14.2.4.2d	Table 14.2.4.2d. Non-TF Endogenous Thrombin Potential Parameters (Efficacy Population)
Table 14.2.4.2e	Table 14.2.4.2e. Endogenous Thrombin Potential by FXa Inhibitor Over Time (Efficacy Population)
Table 14.2.4.3a	Table 14.2.4.3a. Tissue Factor Pathway Inhibitor (TFPI) Over Time (Safety Population)
Table 14.2.4.3b	Table 14.2.4.3b. Tissue Factor Pathway Inhibitor (TFPI) Over Time (Efficacy Population)
Table 14.2.4.4	Table 14.2.4.4. Antithrombin III (ATIII) Over Time (Efficacy Population)

Table Number	Table Title
Table 14.2.4.5	Table 14.2.4.5. Anti-factor IIa Activity (ANTI-IIA, IU/mL) Over Time of Enoxaparin Patients (Safety Population)
Table 14.2.4.6	Table 14.2.4.6. Hemostatic Efficacy of Patients with ICH at 12 Hours Post Andexanet (Efficacy Population)
Table 14.2.4.7a	Table 14.2.4.7a. Proportion of Patients Received Red Blood Cell Transfusion Post Andexanet (Efficacy Population)
Table 14.2.4.7b	Table 14.2.4.7b. Proportion of Patients Received Red Blood Cell Transfusion Post Andexanet (Safety Population)
Table 14.2.4.8a	Table 14.2.4.8a. Clinical Neurologic Status (Modified Rankin Score [mRS]) for Patients with ICH (Efficacy Population)
Table 14.2.4.8b	Table 14.2.4.8b. Clinical Neurologic Status (Glasgow Coma Scale & National Institutes of Health Stroke Scale) for Patients with ICH (Efficacy Population)
Table 14.3.1.1	Table 14.3.1.1. Summary of Adverse Events (Safety Population)
Table 14.3.1.2	Table 14.3.1.2. Summary of Adverse Events by Andexanet Generation (Safety Population)
Table 14.3.1.3a1	Table 14.3.1.3a1. Most Common ≥ 10% TEAE by MedDRA Primary System Organ Class (Safety Population)
Table 14.3.1.3a2	Table 14.3.1.3a2. Most Common ≥ 3% TEAE by Preferred Term (Safety Population)
Table 14.3.1.3b1	Table 14.3.1.3b1. TEAE by MedDRA Primary System Organ Class, Andexanet Generation, and Severity (Safety Population)
Table 14.3.1.3b2	Table 14.3.1.3b2. TEAE by MedDRA Preferred Term, Andexanet Generation, and Severity (Safety Population)
Table 14.3.1.3c	Table 14.3.1.3c. TEAE by FXa Inhibitor, MedDRA Primary System Organ Class, Preferred Term, and Andexanet Generation (Safety Population)
Table 14.3.1.3d	Table 14.3.1.3d. TEAE by Age, MedDRA Primary System Organ Class, Preferred Term, and Andexanet Generation (Safety Population)
Table 14.3.1.3e	Table 14.3.1.3e. TEAE by Sex, MedDRA Primary System Organ Class, Preferred Term, and Andexanet Generation (Safety Population)
Table 14.3.1.3f	Table 14.3.1.3f. TEAE by Race, MedDRA Primary System Organ Class, Preferred Term, and Andexanet Generation (Safety Population)
Table 14.3.1.3g	Table 14.3.1.3g. TEAE by MedDRA Preferred Term (Safety Population)
Table 14.3.1.4a	Table 14.3.1.4a. TEAE Overview by FXa Inhibitor (Safety Population)
Table 14.3.1.4b	Table 14.3.1.4b. TEAE Overview by Age Category (Safety Population)
Table 14.3.1.4c	Table 14.3.1.4c. TEAE Overview by Sex (Safety Population)
Table 14.3.1.4d	Table 14.3.1.4d. TEAE Overview by Race (Safety Population)
Table 14.3.1.4e	Table 14.3.1.4e. TEAE by Severity and Age (Safety Population)
Table 14.3.1.4f	Table 14.3.1.4f. TEAE by Severity and Sex (Safety Population)
Table 14.3.1.4g	Table 14.3.1.4g. TEAE by Severity and Race (Safety Population)
Table 14.3.1.4h	Table 14.3.1.4h. Number of Patients with TEAEs by Age (Safety Population)

Table Number	Table Title
Table 14.3.1.4i	Table 14.3.1.4i. Number of Patients with TEAEs by Sex (Safety Population)
Table 14.3.1.4j	Table 14.3.1.4j. Number of Patients with TEAEs by Race (Safety Population)
Table 14.3.1.5a	Table 14.3.1.5a. Treatment Related TEAE by MedDRA Preferred Term (Safety Population)
Table 14.3.1.5b	Table 14.3.1.5b. Treatment Related TEAE by FXa Inhibitor (Safety Population)
Table 14.3.1.5c	Table 14.3.1.5c. Treatment Related TEAE by Age (Safety Population)
Table 14.3.1.5d	Table 14.3.1.5d. Treatment Related TEAE by Sex (Safety Population)
Table 14.3.1.5e	Table 14.3.1.5e. Treatment Related TEAE by Race (Safety Population)
Table 14.3.1.5f	Table 14.3.1.5f. Time (days) of Treatment Related TEAE by FXa Inhibitor (Safety Population)
Table 14.3.1a	Table 14.3.1a. Study Drug Exposure (Safety & Efficacy Population)
Table 14.3.1b	Table 14.3.1b. Study Drug Exposure by Generation (Safety Population)
Table 14.3.1c	Table 14.3.1c. Study Drug Exposure by FXa Inhibitor (Safety Population)
Table 14.3.1d	Table 14.3.1d. Study Drug Exposure by Bleed Type (Safety Population)
Table 14.3.2.1a	Table 14.3.2.1a. Adjudicated Reason of Deaths (Safety Population)
Table 14.3.2.1b	Table 14.3.2.1b. Demographics of Patients Who Died (Safety Population)
Table 14.3.2.1c	Table 14.3.2.1c. Number of Thrombotic Events and Deaths Before Hospital Discharge (Safety Population)
Table 14.3.2.2	Table 14.3.2.2. Number of Deaths by Bleed Type, FXa Inhibitor, and Andexanet Generation (Safety Population)
Table 14.3.2.3	Table 14.3.2.3. Mortality Rates Stratified by Age Decile (Safety Population)
Table 14.3.2.4	Table 14.3.2.4. Age of Patients Who Died by Andexanet Generation (Safety Population)
Table 14.3.2.5	Table 14.3.2.5. Time to Death (Days) by Generation with FXa Inhibitor (Safety Population)
Table 14.3.2.7a	Table 14.3.2.7a. TE-SAE by MedDRA Primary System Organ Class and Preferred Term (Safety Population)
Table 14.3.2.7b	Table 14.3.2.7b. TE-SAE Considered Possibly or Probably Related to Andexanet Treatment (Safety Population)
Table 14.3.2.7c	Table 14.3.2.7c. TE-SAE by FXa Inhibitor (Safety Population)
Table 14.3.2.7d	Table 14.3.2.7d. TE-SAE by Age (Safety Population)
Table 14.3.2.7e	Table 14.3.2.7e. TE-SAE by Sex (Safety Population)
Table 14.3.2.7f	Table 14.3.2.7f. TE-SAE by Race (Safety Population)
Table 14.3.2.9	Table 14.3.2.9. Characteristics of Thrombotic Events Stratified by TE Type[1] (Safety Population)
Table 14.3.2.10	Table 14.3.2.10. Comparison of Thrombotic Events vs. No Events Stratified by Bleed Type (Safety Population)
Table 14.3.2.11	Table 14.3.2.11. Comparison of Patients with Thrombotic Events vs. Patients Without Thrombotic Events (Safety Population)

Table Number	Table Title
Table 14.3.2.12	Table 14.3.2.12. Characteristics of Thrombotic Events and Re-anticoagulation Stratified by Generation and Bleed Type (Safety Population)
Table 14.3.2.13	Table 14.3.2.13. Thrombotic Events and Re-anticoagulation (Safety Population)
Table 14.3.2.14	Table 14.3.2.14. Thrombotic Events (Safety Population)
Table 14.3.2.15a	Table 14.3.2.15a. Analysis of Hematoma Expansion in Patients with Intraparenchymal Volume (mL) (Safety Population)
Table 14.3.2.15b	Table 14.3.2.15b. Analysis of Hematoma Expansion in Patients with Intraparenchymal Volume (mL) (Efficacy Population)
Table 14.3.4.1	Table 14.3.4.1. Antibodies to Andexanet, FX, FXa (Safety Population)
Table 14.3.4.2a	Table 14.3.4.2a. Systolic Blood Pressure and Diastolic Blood Pressure Over Time After Andexanet Treatment by Bleed Type (Safety Population)
Table 14.3.4.2b	Table 14.3.4.2b. Heart Rate and Respiratory Rate Over Time After Andexanet Treatment by Bleed Type (Safety Population)
Table 14.3.4.3	Table 14.3.4.3. Baseline and Change from Baseline in Hemoglobin at 12 hours Post Andexanet Treatment (Safety Population)

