11.8. Subgroup Analyses

Consistency of efficacy across important subgroups will be investigated.

In addition to the above analyses, primary efficacy and safety will be summarized, at a minimum, for the following subgroups: sex (male, female), race (any race with at least 5 members, all others combined), age (< 65 years, \ge 65 years, \ge 75 years), anticoagulant, type of bleed (e.g., ICH vs. GI vs. other), and requirement for re-dosing. In addition, hemostatic efficacy in ICH patients at higher risk for hematoma expansion will be evaluated as an exploratory efficacy analysis. Patients at higher risk for hematoma expansion will be defined by the following criteria:

For intracerebral/intraparenchymal bleeding, volume of hematoma > 3 mL, OR
For subdural bleeding, thickness of hematoma > 10 mm or midline shift > 5 mm, OR
For subarachnoid bleeding, thickness of hematoma > 10 mm.

A minimum of 50 efficacy evaluable patients meeting these criteria, as determined by the core lab, will be enrolled in this subgroup.

Screening for differential treatment effects on the primary endpoints across subgroups will be conducted using a formal test of interaction obtained from a logistic regression model.

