5.16. Safety analysis

All safety analyses will be conducted using the Safety analysis population. Unless otherwise indicated, all analyses will be presented for an overall population (pooled across the different inhibitors) and stratified by the different inhibitors.

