5.16.2. Adverse Events

A TEAE is defined as any AE that has an onset on or after the first dose of andexanet, or any pre-existing condition that has worsened on or after the first dose of andexanet. TEAEs will be attributed to andexanet using the following rules:

A treatment-related adverse event is defined as a TEAE possibly or probably related to and exanet. TEAEs with missing relationship will be counted as being treatment-related for analysis purposes.

The incidence of TEAEs, treatment-related AEs, TEAEs that led to early withdrawals, and serious AEs (SAEs) will also be summarized by maximum severity and most-related relationship to and exanet by MedDRA primary system organ class and preferred term. The summary will include the total number and percentage of patients reporting a particular event. In counting the number of events reported, a continuous event, i.e. reported more than once and which did not cease, will be counted only once; non-continuous adverse events reported several times by the

same patient will be counted as multiple events. AEs occurring prior to and examet treatment will be listed separately. Adverse events will be coded using MedDRA version 18.0.

Narratives of deaths, serious and other significant adverse events will be provided in the relevant section of the study report.

A complete patient listing of all adverse events will be provided in Appendix 16.2 to the study report. This listing will include treatment, AE verbatim, MedDRA primary system organ class and preferred term, the day of onset and cessation of event relative to first dosing of andexanet, duration of AE, whether serious (yes/no), severity, relationship to andexanet, action taken and outcome, treatment emergent and non-treatment emergent events will be listed separately.

AEs of special interest will be summarized. As defined in the protocol, AEs of special interest are thrombotic or embolic events of any severity, whether serious or not, and infusion reactions that are either serious or severe or both.

Adverse events will be summarized for the following subgroups of sex (male, female), race (any race with at least 5 members, all others combined), age deciles, and FXa inhibitor.

5.16.3. **Deaths**

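### The protocol makes type of bleed and requirement for re-dosing minimum safety subgroups, but the SAP summarises adverse events by neither and records no departure

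*SAP*

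**What the plan says.** Protocol 11.8 sets a floor for subgroup reporting: "primary efficacy and safety will be summarized, at a minimum, for the following subgroups: sex (male, female", followed by race, age and anticoagulant, and closing with "type of bleed (e.g., ICH vs. GI vs. other), and requirement for re-dosing". That makes six subgroups, and the sentence applies them to safety as well as to primary efficacy.

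SAP 5.16 sets a default for safety outputs: unless otherwise indicated, "all analyses will be presented for an overall population (pooled across the different inhibitors) and stratified by the different inhibitors". SAP 5.16.2 then gives the list for adverse events: "Adverse events will be summarized for the following subgroups of sex (male, female", and "race (any race with at least 5 members, all others combined), age deciles, and FXa inhibitor". Neither type of bleed nor re-dosing appears.

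The table list in SAP 7.0 is consistent with this. Its TEAE and SAE titles are by inhibitor (for example "TEAE Overview by FXa Inhibitor (Safety Population"), age, sex, race, severity or product generation, or have no split. SAP 5.17.2, which describes the main changes to the analysis plan, does not mention dropping the two subgroups.

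**The concern.** The trial has no control arm (Protocol 3.4.1), so an adverse-event rate has no internal comparator and must be read against the patients who produced it. Protocol 3.4.2 says that ICH has a markedly worse outlook than other major bleeding and that enrolment is enriched for it, with other bleed types open to capping. The share of ICH patients is therefore partly a result of enrolment policy. An overall TEAE, SAE or treatment-related AE rate averages over that mix.

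The same problem affects the split that the SAP does plan. If the inhibitor groups differ in their proportion of ICH, a by-inhibitor AE table mixes any effect of inhibitor with the effect of bleed type, and no planned AE table allows a reader to separate them.

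Re-dosed patients receive a further bolus and infusion after a recurrent or new bleed. The protocol asked for their safety to be summarised, and SAP 5.16.1 provides only a listing of who they were and why they were re-dosed.

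**Working it through.** The plan states no figure to reproduce. The check compares texts and counts tables.

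**1. Protocol minimum against the SAP's adverse-event subgroups**

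| Protocol 11.8 | SAP 5.16.2 |
|---|---|
| Sex | Yes |
| Race | Yes |
| Age | Yes, as deciles rather than the protocol's age bands |
| Anticoagulant | Yes, as FXa inhibitor |
| Type of bleed (ICH, GI, other) | No |
| Requirement for re-dosing | No |

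Four of six are carried over; two are missing.

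**2. Listed tables**

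AE tables 14.3.1.1 to 14.3.1.5f number 27, and SAE tables 14.3.2.7a to f number 6: 27 + 6 = 33. By main split:

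- none: 7
- generation only: 3
- inhibitor: 5
- age: 6
- sex: 6
- race: 6
- type of bleed: 0
- re-dosing: 0

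Check: 7 + 3 + 5 + 6 + 6 + 6 = 33.

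**3. Where the SAP does use type of bleed for safety**

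- 30-day deaths: SAP 5.16.3 and Table 14.3.2.2.
- Adjudicated thrombotic events: SAP 5.16.4 and Tables 14.3.2.10 and 14.3.2.12.
- Exposure: SAP 5.16.1 and Table 14.3.1d.
- Red-cell transfusion, listed as a safety endpoint in SAP 4.6.3: SAP 5.15.1.7, for the safety population.
- Vital signs: Tables 14.3.4.2a and b, in the table list only.

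For the broader, FDA-recommended thrombotic-event definition, SAP 5.16.4 specifies a proportion of the safety population with an exact interval and no bleed-type split. Requirement for re-dosing is not a subgroup anywhere in SAP 5.16.

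**4. How pooling acts on a by-inhibitor comparison**

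Let an event have rate p1 in ICH and p2 in other bleeds, the same for every inhibitor, and let s be the ICH share.

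Pooled rate = s·p1 + (1 − s)·p2.

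Difference between inhibitors A and B = (sA − sB)·(p1 − p2).

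With purely assumed values p1 = 30%, p2 = 5%, sA = 70% and sB = 50%:

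- A: 0.70 × 30 + 0.30 × 5 = 22.5%
- B: 0.50 × 30 + 0.50 × 5 = 17.5%
- Difference: 0.20 × 25 = 5.0 points, with no inhibitor effect at all.

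If either the shares or the rates coincide, the difference is zero. The documents give neither, so this shows the mechanism and does not estimate its size.

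**The case against.** The strongest reply is that the SAP does report key safety outcomes by bleed type, and that Protocol 11.8 speaks of safety in general, not of adverse-event tables in particular. This has force against a broad claim. Deaths are fatal SAEs, and thrombotic events are AEs of special interest, so it would be wrong to say that serious outcomes in ICH and GI patients are never shown separately. The clinical course of ICH is also covered by the GCS, mRS and NIHSS analyses (SAP 5.15.1.10). But Protocol 11.5.5 and 11.7.1 count AEs among the safety endpoints, and nothing in 11.8 exempts them. For re-dosing the reply fails, since no safety outcome is split by it.

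A second reply is that the table list proves little. SAP 7.0 calls it a sample that will not be updated, and it still carries generation splits that SAP 5.17.2 says were removed. Figure 14.3.1.3, on events by subgroup, names neither the events nor the subgroups. That is correct, and a reader should not infer from the list that such tables will be absent from the report. The point rests on SAP 5.16.2, which has the same gap in its text. SAP 5.1 permits additional tables in the study report, with justification, but that permission does not commit the sponsor to a stated protocol minimum.

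A reader might also infer that AEs must be shown by andexanet dose, because deaths and thrombotic events are. Protocol 11.8 does not list dose. Dose is also not randomised: it follows from the inhibitor and the size and timing of its last dose, so AE rates by dose would be hard to interpret. It is an optional addition.

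**Conclusion.** The point holds as a mismatch between protocol and SAP. Two of the six minimum safety subgroups, type of bleed and requirement for re-dosing, are missing from the adverse-event plan, and the departure is neither recorded nor justified. Followed as written, the SAP gives overall TEAE, SAE and treatment-related AE rates only pooled across bleed types, and by-inhibitor AE rates that are confounded with bleed mix to an unknown degree.

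The documents do not support a statement that the ICH adverse-event rate will be understated by a given number of points. That would need assumed event rates, and the ICH share in the safety population is not given: the minimum of about 110 ICH patients refers to efficacy-evaluable patients, and the 477 in SAP 1.0 are all locked patients, so their ratio is not that share.

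These are descriptive summaries and do not bear on either primary conclusion. The change should be made because the protocol promised these summaries and they can be produced from data already collected. The conclusion assumes that safety in Protocol 11.8 includes adverse events, as Protocol 11.5.5 and 11.7.1 indicate.

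**What to change.** In SAP 5.16.2, add type of bleed (ICH, GI, Other, as classified in the current SAP) and requirement for re-dosing (yes, no) to the adverse-event subgroups. Produce the TEAE overview, the SAE summary and the treatment-related TEAE summary by each. If the sponsor prefers not to, it should record the departure from Protocol 11.8 in SAP 5.17.2 with a reason.

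The cost is a wording change and a few more descriptive tables. Bleed type is already derived for the death and thrombotic-event analyses, and re-dosed patients are already identified for the listing in SAP 5.16.1. The re-dosed group is likely to be small, so its table should give counts with denominators and be read descriptively. AE summaries by andexanet dose may be added as an option, labelled as non-randomised and not required by the protocol.
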